3. GENERAL INFORMATION

Objective	To evaluate visual outcomes and quality of vision following bilateral implantation of the Clareon PanOptix intraocular lens (IOL) targeted for emmetropia.
	The hypothesis is that the Clareon™ PanOptix™ Trifocal IOL will provide good overall quality of vision and visual outcomes.
Test Article(s)	The Clareon™ PanOptix™ Trifocal (toric and non-toric models)
Control Article(s)	None.
Sample size	70 eyes of 35 subjects
Study Population	Subjects \geq 40 years of age presenting for cataract surgery who are interested in reducing their dependence on spectacles at all distances, and who are appropriate candidates for trifocal lens implantation.
Number of sites	One
Study Design	Prospective, non-randomized, single-arm study.
Masking	None
Variables	Primary: Binocular distance-corrected near (40 cm) visual acuity), 1 and 3-months postop Secondary: 
• Bilateral visual acuity outcomes (uncorrected and best-distance-corrected) at distance (6m), intermediate (60 cm), and near (40 cm), 1 and 3-months postop• Manifest refraction (residual spherical equivalent refraction, residual sphere, and residual astigmatism), 1 and 3-months postop• Binocular, distance corrected defocus curve at 3 month post-operatively, using standard parameters: (+1.00 to -3.00 in 0.50D except +0.50 to -0.50 in 0.25D).• Questionnaire for visual disturbance scores (QUVID)

- Patient satisfaction questionnaire scores (IOLSAT)

Exploratory:

- Binocular DCNVA at 33cm, 1 and 3-months post-operatively.

Duration / Follow-up Preoperative to 3 months postoperative

The study will be registered with clinicaltrials.gov.

The study will be conducted in compliance with the protocol, GCP and applicable regulatory requirements

5. INTRODUCTION

Previous studies have shown that the AcrySof® PanOptix™ IOL (Alcon Vision LLC, Fort Worth, Texas, USA) provides good visual outcomes for patients at distance, intermediate and near.^{1,2} We are interested in determining the binocular distance-corrected near (40 cm) visual acuity when the Clareon™ PanOptix™ IOL is implanted bilaterally.

6. OBJECTIVE(S)

To evaluate visual outcomes and quality of vision following bilateral implantation of the Clareon PanOptix intraocular lens (IOL) targeted for emmetropia.

7. SUBJECTS

7.1. *Subject Population*

Eligible test subjects will be presenting for cataract surgery who are interested in a reduced dependence on spectacles for near, intermediate and distance vision, and who are considered appropriate candidates for trifocal lens implantation.

A total of 70 eyes of 35 subjects at one site will be enrolled. Both eyes of a subject must be enrolled. Subjects must meet the inclusion criteria. Prior to enrollment, subjects will be provided information on the study and asked to sign a patient information and consent form to participate. The patient information and consent form will be approved by an appropriate ethics committee.

7.2. *Inclusion Criteria*

Subjects are eligible for the study if they meet the following criteria:

Note: Ocular criteria must be met in both eyes.

- Presenting for uncomplicated bilateral cataract surgery and have an interest in spectacle independence using a trifocal IOL
- Meet the requirements for on-label implantation of the trifocal IOL
- Gender: Males and Females.
- Age: 40 or older.
- Willing and able to provide written informed consent for participation in the study.
- Willing and able to comply with scheduled visits and other study procedures.
- Have good ocular health, with no pathology that compromises visual acuity (outside of residual refractive error and cataract).
- Expected visual potential of 20/25 Snellen (0.10 logMAR) or better in each eye.

- All eyes will be in the range of availability for Clareon PanOptix IOL and Clareon PanOptix Toric IOL. For cylinder below the Toric IOL indication (T3), an LRI will be used during surgery.

7.3. Exclusion Criteria

If any of the following exclusion criteria are applicable to the subject or either eye, the subject should not be enrolled in the study.

- Patients with any corneal pathology (including corneal dystrophies, scarring, severe dry eye syndrome, irregular astigmatism, HOA) limiting or affecting visual potential.
- Patients with previous corneal refractive surgery.
- Patients with pre-existing ocular pathology, including maculopathy, ARMD, ERM, prior RD, and glaucoma limiting or affecting visual potential.
- Subjects who have an unstable acute or chronic disease or illness that would confound the results of this investigation (e.g., immunocompromised, connective tissue disease, clinically significant atopic disease, diabetes, and any other such disease or illness), that are known to affect postoperative visual acuity.
- Participation in any investigational drug or device trial within the previous 30 days prior to the start date of this trial (or currently participating).

The principal investigator reserves the right to declare a patient ineligible or non-evaluable based on medical evidence that indicates they are unsuitable for the trial.

Pregnancy has a known effect on the stability of refractions and visual acuity. As such, subjects who become pregnant during the study will not be discontinued but their data may be excluded from analyses of effectiveness.

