8. STUDY DESIGN

8.1. Study Design

This study is a single-arm unmasked clinical evaluation study of binocular distance-corrected near (40 cm) visual acuity after successful bilateral cataract surgery. Subjects will be assessed pre-operatively, operatively and at 1 day, 1 month and 3 months post-operatively. Clinical evaluations will include administration of a visual disturbance questionnaire (QUVID), and a satisfaction questionnaire (IOLSAT), as well as measurement of bilateral visual acuity and manifest refraction.

The primary outcome measure will be the binocular distance-corrected near (40 cm) visual acuity at 1 and 3 months postoperative.

Secondary outcome measures are as follows:

- Bilateral visual acuity outcomes (uncorrected and best-distance-corrected) at distance (6m), intermediate (60 cm), and near (40 cm), 1 and 3-months postop
- Manifest refraction (residual spherical equivalent refraction, residual sphere, and residual astigmatism), 1 and 3-months postop
- Binocular, distance corrected defocus curve at 3 month post-operatively, using standard parameters: (+1.00 to -3.00 in 0.50D except +0.50 to -0.50 in 0.25D).
- Questionnaire for visual disturbance scores (QUVID)
- Patient satisfaction questionnaire scores (IOLSAT)

Exploratory outcome measures are as follows:

- Binocular DCNVA at 33cm, 1 and 3-months post-operatively

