9.2.1. Preoperative

At the preoperative exam, subjects will be consented, qualified for the study (compared with inclusion/exclusion criteria), and assigned a study ID/subject number. Subject numbers will be assigned sequentially at each site in the order of enrollment. Pre-operative qualification should take place no more than 30 days prior to surgery.

A medical history will be taken and exams will include the tests described below:

- manifest refraction,
- visual acuity
- preoperative QUVID questionnaire
- preoperative IOLSAT questionnaire

In addition, all site-specific, routine, usual standard of care preoperative measures should be undertaken.

Measurements should be made as described in section 9.3 below.

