9.2.2. Operative (Surgery)

All subjects will undergo cataract surgery with implantation of the Clareon PanOptix IOL. The surgeon's usual standard of care with regard to treatment and medication will be used for all study subjects. Surgery planning and IOL power calculation will be performed using the surgeon's preferred method, with an initial a-constant provided by Alcon. If a toric IOL is used, planning will be performed with the Alcon Toric calculator that takes the effects of posterior corneal astigmatism into account.

Surgical findings will be recorded and any adverse events/serious adverse events (AEs/ SAEs) occurring during surgery will be noted at this visit. Any other problems during surgery and comments regarding surgery will be documented.

Any subject whose surgery is not completed successfully will be documented in the appropriate case report form. These subjects will be monitored for safety but clinical performance data may be excluded from the analysis.

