10. ANALYSIS PLAN

10.1. Analysis Data Sets

All subjects who are enrolled in the study will be evaluated for safety. Efficacy analyses will be performed based on data from those eyes where uncomplicated cataract surgery with PanOptix IOL implantation was completed.

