10.2. Statistical Methodology

A summary of the data will be prepared for all measurement time points. Summaries of the changes observed between the 1-month and 3-month post-operative visits will also be summarized.

For variables measured on a continuous scale, these summaries will include the sample size, as well as the mean, standard deviation, median, minimum, and maximum. For variables measured on a categorical scale, summaries will provide the number and percentage of subjects who provided each score (or change in scores). These summaries will be provided for all eyes completing the study.

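### Section 7.3 lets an unmasked investigator declare subjects non-evaluable with no time limit, and Sections 10.1 and 10.2 do not settle whether those subjects are analysed

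*Combined protocol and SAP*

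**What the plan says.** **Section 7.3 (Exclusion Criteria).** After the list of criteria, the principal investigator "reserves the right to declare a patient ineligible or non-evaluable based on medical evidence that indicates they are unsuitable for the trial". The section then says that "subjects who become pregnant during the study will not be discontinued but their data may be excluded from analyses of effectiveness".

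**Section 9.2.1 (Preoperative).** Eligibility is checked before surgery: "subjects will be consented, qualified for the study (compared with inclusion/exclusion criteria), and assigned a study ID/subject number". Section 9.1 makes meeting the criteria a condition of enrolment.

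**Section 10.1 (Analysis Data Sets).** "Efficacy analyses will be performed based on data from those eyes where uncomplicated cataract surgery with PanOptix IOL implantation was completed". It mentions neither a non-evaluable status nor pregnancy. Safety covers everyone enrolled.

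**Section 10.2 (Statistical Methodology).** "These summaries will be provided for all eyes completing the study".

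**Section 9.2.2 (Operative).** For subjects whose surgery is not completed successfully, "clinical performance data may be excluded from the analysis".

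**Section 8.1 (Study Design).** "This study is a single-arm unmasked clinical evaluation study of binocular distance-corrected near (40 cm) visual acuity after successful bilateral cataract surgery".

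**The concern.** Eligibility is settled at the preoperative visit, so a power to call someone non-evaluable has its main use after enrolment. Section 7.3 does not say what counts as medical evidence, by when the decision must be made, who else reviews it, or whether it must be made without sight of acuity and questionnaire results. No other section supplies these limits.

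The entry criteria lie close to the outcome. They ask for an expected potential of 0.10 logMAR or better in each eye and no pathology that limits visual potential. An eye that sees poorly after surgery is the one most likely to be searched for a cause, and dry eye or a macular finding could then be read as showing that the subject was never suitable. Declarations made in good faith would still come mostly from the poor end of the primary outcome. There is no control arm in which the same thing happens, and the stated hypothesis is that the lens performs well. Section 8.2 expects no bias; its measures standardise testing and instructions and do not touch exclusions.

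The power does not depend on how surgery went, so tightening the surgical clause in 9.2.2 would leave it open.

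**Working it through.** **1. The plan's own figure.** Section 11 wants 32 subjects after 10% dropout and enrols 35. 32 / (1 − 0.10) = 35.6, which rounds up to 36; in reverse, 35 × 0.90 = 31.5, about 32. The stated 35 is reproduced to within one subject. Section 11 gives no SD, effect size or power, so nothing further can be reproduced.

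**2. The same subject under each section.** Take a subject with uncomplicated bilateral implantation, poor month-3 near acuity, and a finding made after surgery that the investigator regards as showing unsuitability.

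| Section | Status of this subject |
|---|---|
| 7.3 | may be declared non-evaluable; consequence for the analysis not stated |
| 10.1 | in the efficacy set |
| 10.2 | in the summaries if the study was completed |

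A subject who becomes pregnant is likewise optional under 7.3 and included under 10.1. One who is successfully implanted but leaves after month 1 is in under 10.1 and out under 10.2. Two analysts could report different subjects and both claim to follow the plan.

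**3. Size, as a ceiling.** Inputs: n = 35 (Section 11). Assumptions: normally distributed acuity, one binocular value per subject, and the k removed subjects are exactly the k worst.

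In a simulation of 200,000 samples of 35 from N(0,1), the three most extreme values average 2.11, 1.69 and 1.45 SD. The shift in the mean is the sum of the k removed values divided by (35 − k):

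- k = 1: 2.11 / 34 = 0.062 SD
- k = 2: (2.11 + 1.69) / 33 = 3.80 / 33 = 0.115 SD
- k = 3: (2.11 + 1.69 + 1.45) / 32 = 5.25 / 32 = 0.164 SD

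The simulated ratios of remaining SD to full SD are 0.940, 0.899 and 0.866, a shrinkage of about 6%, 10% and 13%.

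The standard error at n = 35 is 1/√35 = 0.169 SD, so three removals shift the mean by 0.164 / 0.169 = 0.97 SE. Using n = 32, the SE is 0.177 SD and the ratio is 0.93.

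**4. In logMAR.** The documents give no SD. Assuming 0.08 to 0.12 logMAR, three removals shift the mean by 0.164 × 0.08 = 0.013 to 0.164 × 0.12 = 0.020 logMAR. For comparison, the 95% half-width at n = 35 is 1.96 × 0.08/√35 = 0.027 to 1.96 × 0.12/√35 = 0.040 logMAR.

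**The case against.** The strongest reply is that the clause is narrower than it looks. It sits among the entry criteria, it requires medical evidence of unsuitability, and Sections 9.1 and 9.2.1 place eligibility before surgery. This stands in part. A reader might infer that the protocol authorises removal at any time, including once results are known, or that eligibility as such can be reopened. The documents do not say so: 7.3 is silent on timing, and a finding of ineligibility is naturally a preoperative one. What remains is that non-evaluable is undefined, plausibly acts later, and has no time limit, so late removal is not prevented.

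A second reply is that 10.1 is definite on its face. It is, if read alone. The difficulty is that it is silent about a status 7.3 creates, and that 10.2 names another set.

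A third is that the effect is small. Also fair: 0.020 logMAR is one fifth of the 0.10 logMAR potential criterion and below the 95% half-width. It is also a ceiling, since real removals would rarely be exactly the worst subjects. A reader might note that three removals equal the gap between 35 and 32, but Section 11 allows that gap for dropout and does not sanction investigator removals.

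On pregnancy, few cases are likely among cataract patients aged 40 or older. The documents do not support the inference that pregnancy at entry ought to be an exclusion; the point is only that an optional data exclusion needs a fixed rule.

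**Conclusion.** The concern holds in this form: an undefined and undated power in 7.3, an optional pregnancy exclusion beside it, and analysis sets in 10.1 and 10.2 that match neither 7.3 nor each other. Together they let the efficacy population depend on judgement made with knowledge of the outcome.

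If exercised selectively, the bias is one-directional: a better mean and an SD that is too small. The ceiling for three of 35 is 0.16 SD and a 13% smaller SD, given normality and removal of exactly the worst subjects. The logMAR range of 0.013 to 0.020 also rests on the assumed SD.

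A reader might infer an inflated type I error or a study conclusion that could flip. The documents do not support that. There is no comparator and no performance goal, and the planned tests are within-subject changes between visits. The safety set is unaffected. But in a mainly descriptive study the mean and SD are the result, so an inexpensive correction should be made.

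**What to change.** - **7.3:** limit declarations of ineligibility to the time before first-eye surgery.
- **10.1:** define the efficacy set by subject, because the primary outcome is binocular: all subjects with uncomplicated bilateral PanOptix implantation and available postoperative data.
- **10.2:** use the same set in place of completers, with the number contributing at each visit, so that someone who leaves after month 1 still counts at month 1.
- **After surgery:** remove no subject in that set for suitability, later-discovered ineligibility or pregnancy. List such subjects with date and reason, and label any analysis without them as a sensitivity analysis.
- **Second eye:** eyes are operated on at separate visits, so report subjects who do not receive the second implant separately, with the reason.

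If the sponsor wants to keep a non-evaluable status, a weaker alternative is to define it by objective criteria, with each decision documented before postoperative outcomes are reviewed.

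The cost is a few sentences in 7.3, 10.1 and 10.2, one listing and, if wanted, one extra summary table. The downside is that a truly unsuitable implanted subject stays in the main summary, which may look slightly less favourable; the sensitivity analysis shows by how much.

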8. STUDY DESIGN

8.1. Study Design

This study is a single-arm unmasked clinical evaluation study of binocular distance-corrected near (40 cm) visual acuity after successful bilateral cataract surgery. Subjects will be assessed pre-operatively, operatively and at 1 day, 1 month and 3 months post-operatively. Clinical evaluations will include administration of a visual disturbance questionnaire (QUVID), and a satisfaction questionnaire (IOLSAT), as well as measurement of bilateral visual acuity and manifest refraction.

The primary outcome measure will be the binocular distance-corrected near (40 cm) visual acuity at 1 and 3 months postoperative.

Secondary outcome measures are as follows:

- Bilateral visual acuity outcomes (uncorrected and best-distance-corrected) at distance (6m), intermediate (60 cm), and near (40 cm), 1 and 3-months postop
- Manifest refraction (residual spherical equivalent refraction, residual sphere, and residual astigmatism), 1 and 3-months postop
- Binocular, distance corrected defocus curve at 3 month post-operatively, using standard parameters: (+1.00 to -3.00 in 0.50D except +0.50 to -0.50 in 0.25D).
- Questionnaire for visual disturbance scores (QUVID)
- Patient satisfaction questionnaire scores (IOLSAT)

Exploratory outcome measures are as follows:

- Binocular DCNVA at 33cm, 1 and 3-months post-operatively

8.2. Methods Used to Minimize Bias

As a single-arm study there is no expected bias. Patient selection will be based on the patient's interest and the surgeon's opinion as to whether they are a suitable candidate for trifocal or trifocal toric IOL implantation.

The measurement of visual acuity will be conducted in a systematic fashion to minimize bias. Individuals conducting visual acuity measures will be instructed to perform the same testing in the same fashion for all subjects, with the same level of encouragement to subjects. Questionnaire instructions will be provided to all patients in a similar manner.

All data collection will be completed through provided Case Report Forms (CRFs) or computer files generated by automated test equipment. All site personnel involved in the study will be trained in regard to conducting study-specific procedures.

9. STUDY PROCEDURE

9.1. Informed Consent / Subject enrollment

No subject will be enrolled into the study who does not meet the inclusion/exclusion criteria and does not sign the current approved informed consent document. Informed consent will be obtained prior to collecting any data for the study. The original signed documents will be maintained by the investigator as a permanent part of the subject's medical records. A signed copy will be provided to the subject.

9.2. Visits and Examinations

Subjects will participate in seven study visits, one eye per visit for bilateral surgery. Visits will include an uptake visit, two operative visits, and 4 total postoperative visits (Visit numbers 1-5 below). The visit schedule, complete with window and associated

CRF forms, are displayed in Table 9.2-1. Details of each study visit, including testing to be conducted, are provided below.

Table 9.2-1. Visit Schedule

Visit Number	Visit Name	Visit Window	CRF Number
1	Preoperative	-30 to 0 days from surgery	1
2,2a	Operative	0 from surgery	2,2a
3,3a	1 Day Postoperative	1-2 days postoperative*	3,3a
4	1 Month Postoperative	30 (± 10) days postoperative**	4
5	3 Months Postoperative	90 (± 20) days postoperative**	5

* relative to the operative eye

** relative to the date the last eye is operated on

9.2.1. Preoperative

At the preoperative exam, subjects will be consented, qualified for the study (compared with inclusion/exclusion criteria), and assigned a study ID/subject number. Subject numbers will be assigned sequentially at each site in the order of enrollment. Pre-operative qualification should take place no more than 30 days prior to surgery.

A medical history will be taken and exams will include the tests described below:

- manifest refraction,
- visual acuity
- preoperative QUVID questionnaire
- preoperative IOLSAT questionnaire

In addition, all site-specific, routine, usual standard of care preoperative measures should be undertaken.

Measurements should be made as described in section 9.3 below.

9.2.2. Operative (Surgery)

All subjects will undergo cataract surgery with implantation of the Clareon PanOptix IOL. The surgeon's usual standard of care with regard to treatment and medication will be used for all study subjects. Surgery planning and IOL power calculation will be performed using the surgeon's preferred method, with an initial a-constant provided by Alcon. If a toric IOL is used, planning will be performed with the Alcon Toric calculator that takes the effects of posterior corneal astigmatism into account.

Surgical findings will be recorded and any adverse events/serious adverse events (AEs/ SAEs) occurring during surgery will be noted at this visit. Any other problems during surgery and comments regarding surgery will be documented.

Any subject whose surgery is not completed successfully will be documented in the appropriate case report form. These subjects will be monitored for safety but clinical performance data may be excluded from the analysis.

9.2.3. Postoperative 1 Day

All routine, usual standard of care postoperative measures should be undertaken. In addition, the subject will undergo VA and lens orientation testing in accordance with the specifications below (Section 9.3). Adverse events will be monitored.

9.2.4. Postoperative 1 Month

All routine, usual standard of care postoperative measures should be undertaken. In addition, the subject will undergo a manifest refraction, VA, and lens orientation testing and complete the QUVID and IOLSAT questionnaires (Section 9.3). Any device deficiencies or adverse events will be monitored.

